2.1 PROTOCOL SYNOPSIS

The Protocol Synopsis is included in [Appendix 1](#). For additional details, see the study schedule of assessments in [Appendix 2](#).

2.2 OUTCOME MEASURES

2.2.1 Primary Efficacy Endpoint

The primary efficacy endpoint for this study is OS, defined as the time (in months) from randomization to death from any cause.

2.2.2 Secondary Efficacy Endpoints

Secondary efficacy outcome measures for this study are as follows:

- Progression free survival, defined as the time between the date of randomization and the date of first documented disease progression or death, whichever occurs first. Disease progression will be determined based on investigator assessment with the use of RECIST v1.1.
- ORR, defined as the proportion of patients with an objective response, either a confirmed complete response (CR) or confirmed partial response (PR) observed on two assessment ≥ 28 days apart with the use of RECIST v1.1 as determined by the investigator.
- DOR, defined for patients with an objective response as the time from the first documented objective response to documented disease progression with the use of RECIST v1.1 as determined by the investigator or death from any cause, whichever occurs first.
- Impact on functioning as measured by changes from baseline on the five-item physical functioning sub-scale of the patient-completed European Organization for Research and Treatment of Cancer Quality of Life Core 30 questionnaire (EORTC QLQ-C30).
- Impact on health-related quality of life (HRQoL) as measured by changes from baseline on the two-item global health status/quality of life sub-scale of the EORTC QLQ-C30.

2.2.3 Exploratory Analyses Endpoints

Exploratory analyses endpoints for this study are as follows:

- OS rate at fixed timepoints (e.g., 6, 12, 18, 24 months), defined as the proportion of patients alive at fixed timepoints after randomization estimated using Kaplan-Meier methodology

- PFS rate at fixed time points (e.g., 3, 6, 9, 12 months), defined as the proportion of patients alive and without disease progression as assessed by the investigator in accordance with RECIST v1.1 at fixed time points after randomization estimated using Kaplan-Meier methodology
- Time to response (TTR), defined as the time from randomization to the first occurrence of a CR or PR as determined by the investigator with the use of RECIST v1.1
- Utility scores of the Euro QoL5 Dimensions (EQ-5D-3L) for use in health economic models

Exploratory biomarker endpoints for this study are as follows:

- The following molecular characteristics in tumor samples during pretreatment, on treatment, and at disease progression:
 - Genetic profile, including but not limited to somatic mutations and MSI status or mutation load as identified through next-generation sequencing (NGS) or other genetic analysis
 - Immune contextures, such as programmed death–ligand 1 (PD-L1), CD8 T cells or major histocompatibility complex expression, as identified by immunohistochemistry (IHC) and gene signature profiling
 - CRC molecular subtyping as defined by genetic and RNA and protein profiles
- The relationship between circulating tumor biomarker (including but not limited to carcinoembryonic antigen, tumor-associated mutations in cell-free DNA) and measures of efficacy

2.2.4 Patient-Reported Outcomes Objectives

The additional patient-reported outcome objective of the study is to assess treatment impact and disease symptoms from the sub-scales of the EORTC QLQ-C30 questionnaire that assess diarrhea, constipation, lack of appetite, fatigue, and two additional items from the EORTC item bank that assess bloating and abdominal pain associated with cobimetinib plus atezolizumab compared with regorafenib in patients with metastatic mCRC.

2.2.5 Pharmacokinetic Efficacy Outcome Measures

The pharmacokinetic (PK) outcome measures for this study are the following:

- Plasma concentration of cobimetinib in Arm A
- Serum concentration of atezolizumab in both the atezolizumab + cobimetinib arm (Arm A) and the monotherapy atezolizumab arm (Arm B)

2.2.6 Safety Outcome Measures

The safety outcome measures for this study are the following:

- Incidence, nature, and severity of adverse events (AEs) graded in accordance with the National Cancer Institute Common Terminology Criteria in Adverse Events, Version 4.0 (NCI CTCAE v4.0)

- Changes in vital signs, physical findings, and clinical laboratory results during the course of study
- Incidence of anti-therapeutic antibody (ATA) response to atezolizumab and potential correlation with PK, safety, and efficacy parameters

[figure not shown]
2.3 DETERMINATION OF SAMPLE SIZE

The study will randomize approximately 360 patients, including a minimum of 180 patients with extended RAS-mutant mCRC (assuming a prevalence of at least 50%), to cobimetinib plus atezolizumab (Arm A), atezolizumab monotherapy (Arm B), and regorafenib (Arm C) with the randomization ratio of 2:1:1, respectively.

The type 1 error (α) for the analysis of the primary endpoint of OS in the comparison of Arm A versus Arm C (the control arm) is 0.05 (2-sided). If OS is statistically significant in the comparison of Arm A versus Arm C, then the OS comparison of Arm B versus Arm C will be tested at a 2-sided α -level of 0.05.

The overview of the type 1 error (α) control is shown in [Figure 2](#).

Figure 2 Overview of Hierarchical Testing Sequence for Type 1 Error^a Control (2-Sided)

OS=overall survival

^a OS will be tested at a 2-sided significance level $\alpha=0.05$ only if the result of previous testing is positive (i.e., statistically significant).

The sample size of this study is determined on the basis of the number of events required to demonstrate efficacy with regard to OS in both comparisons (Arm A vs. Arm C and Arm B vs. Arm C).

The estimate of the number of events required to demonstrate efficacy with regard to OS is based on the following assumptions:

- Two-sided significance level of 0.05
- Arm A versus Arm C: 87% power to detect an hazard ratio (HR) of 0.61, corresponding to an improvement in median OS from 6.4 months in Arm C to 10.5 months in Arm A
- Arm B versus Arm C: 80% power to detect an HR of 0.61, corresponding to an improvement in median OS from 6.4 months in Arm C to 10.5 months in Arm B
- No interim analysis for OS

- Dropout rate of 10% in 24 months
- Hierarchical testing of Arm A versus Arm C followed by Arm B versus Arm C to control the overall α level of 5%

With these assumptions, approximately 360 patients in total will be randomized into this study, with approximately 270 patients for the comparison of Arm A versus Arm C and approximately 180 patients for the comparison of Arm B versus Arm C. The OS final analysis will be conducted when there are approximately 235 deaths occurring from all three arms. At this time, it is expected that approximately 178 deaths for the comparison of Arm A versus Arm C and approximately 127 deaths for the comparison of Arm B versus Arm C will have occurred.

The number of events corresponds to a minimum detectable difference in HR of approximately 0.73 for the Arm A versus Arm C comparison and approximately 0.71 for the Arm B versus Arm C comparison.

2.4 ANALYSIS TIMING

2.4.1 Primary Analysis Timing

No interim analyses are planned for the efficacy endpoints. The OS final analysis for the primary comparisons of Arm A versus Arm C and Arm B versus Arm C will be conducted when there are a total of approximately 235 OS events from the study, which is expected to occur approximately 23 months after the first patient is randomized, based on the study assumptions and the projected accrual rate. The number of events, the event ratio, the minimum detectable difference (MDD), and the power for each comparison are summarized in [Table 1](#).

Table 1 Analysis for Overall Survival for Primary Comparisons (Arm A vs. Arm C and Arm B vs. Arm C)

	OS Final Analysis	
	Arm A vs. Arm C	Arm B vs. Arm C
Events (event ratio)	178 (66%)	127 (71%)
MDD in HR	0.73	0.71
Power	87%	80%

FPI=first patient in; HR=hazard ratio; MDD=minimum detectable difference; OS=overall survival; event ratio=number of events / number of patients randomized.

Note: OS final analysis to occur approximately 23 months from FPI.

2.4.2 Analysis Timing for Experimental Arm Comparison

If both of the primary comparisons (i.e., Arm A vs. Arm C and Arm B vs. Arm C) are statistically significant for OS, then OS between the experimental arms (i.e., Arm A vs. Arm B) will be compared at the time of the primary analysis. At this time, a total of approximately 165 OS events are expected from Arms A and B, corresponding to an

MDD in HR of 0.72. The operating characteristics for selected target HRs comparing Arm A with Arm B is presented in [Table 2](#).

Table 2 Operating Characteristics for the Comparison of Arm A versus Arm B with Approximately 165 Overall Survival Events

Target HR	Power	95% CI ^a
0.61	85%	(0.44, 0.84)
0.67	69%	(0.48, 0.93)
0.75	42%	(0.54, 1.04)

FPI= first patient in; HR = hazard ratio; mOS = median overall survival.

^a 95% CI when the target HR is observed.

3. STUDY CONDUCT

3.1 RANDOMIZATION ISSUES

Randomization to arms A, B, and C will occur in a 2:1:1 ratio, respectively, using a permuted-block randomization method. Randomization will be stratified by the following factors:

- Extended RAS mutation status of the tumor (yes vs. no)
- Time since diagnosis of first metastasis (< 18 months vs. ≥ 18 months)

3.2 DATA MONITORING

An Internal Monitoring Committee (IMC) will be used to evaluate safety during the study on a periodic basis until the primary analysis. For details of the IMC, refer to the IMC Charter ([Appendix 4](#)).

4. STATISTICAL METHODS

The analyses described in this SAP will supersede those specified in Protocol GO30182 for the purpose of a regulatory filing.

4.1 ANALYSIS POPULATIONS

4.1.1 Efficacy Analysis Population

The randomized population or intent-to-treat (ITT) population is defined as all randomized patients, whether or not the patient received the assigned treatment.

4.1.2 Pharmacokinetic-Evaluable Population

The pharmacokinetic-evaluable population is defined as all patients who received any dose of study medication and who have at least one post-baseline PK sample available.

4.1.3 Safety Population

Safety analyses will be performed on all randomized patients who received any amount of any component of protocol treatment, with patients grouped as follows:

- Cobimetinib + atezolizumab arm (Arm A): patients who received any amount of cobimetinib
- Atezolizumab arm (Arm B): patients who received any amount of atezolizumab without any amount of cobimetinib
- Regorafenib arm (Arm C): patients who received any amount of regorafenib without any amount of either atezolizumab or cobimetinib.

4.2 ANALYSIS OF STUDY CONDUCT

Study enrollment, major protocol deviations including major deviations of inclusion/exclusion criteria, and reasons for study termination will be summarized overall and by treatment arm for the ITT population. Study treatment administration and reasons for discontinuation from study treatment will be summarized for the Safety population.

4.3 ANALYSIS OF TREATMENT GROUP COMPARABILITY

Demographic characteristics, such as age, race/ethnicity, baseline disease characteristics (e.g., Eastern Cooperative Oncology Group [ECOG] performance status), and stratification factors will be summarized by treatment arms for the ITT population. Descriptive statistics (mean, median, standard deviation, and range) will be presented for continuous data, and frequencies and percentages will be presented for categorical data.

Baseline values are the last available data obtained prior to the patient receiving the first dose of any component of study treatment on Cycle 1, Day 1.

4.4 EFFICACY ANALYSIS

Patients will be grouped for efficacy analyses according to the treatment assigned at randomization, whether or not the assigned treatment was received.

4.4.1 Primary Efficacy Endpoint

The primary efficacy endpoint is OS. Overall survival is defined as the time between the date of randomization and the date of death due to any cause. Data for patients who are not reported as having died at the time of analysis will be censored at the date they were last known to be alive. Data for patients who do not have post-baseline information will be censored at the date of randomization plus 1 day.

Comparisons with respect to OS for each of the two comparisons between treatment arms will be tested based on a stratified log-rank test in the ITT populations in the analysis at the two-sided level of significance as described in Section 2.3. The stratification factors will be those used for randomization (i.e., extended RAS

mutation status (yes vs. no) and time since diagnosis of first metastasis [< 18 months vs. ≥ 18 months]), and will be obtained from the IxRS.

The null and alternative hypotheses can be phrased in terms of the survival functions $S_E(t)$ and $S_C(t)$, where $S_E(t)$ represents the survival function for experimental arm (either Arm A or Arm B) and $S_C(t)$ represents the survival function for Arm C:

$$H_0: S_E(t) = S_C(t) \text{ versus } H_1: S_E(t) \neq S_C(t)$$

The HR (λ_E/λ_C , where λ_E represents the hazard of death in experimental arm [either Arm A or Arm B] and λ_C represents the hazard of death in Arm C, comparing the treatment effect between the two treatment arms) will be estimated using a stratified Cox regression model with the same stratification variables used for the stratified log-rank test, and the 95% CI will be provided. Results from an unstratified analysis will also be provided.

Kaplan-Meier methodology will be used to estimate median OS and to construct survival curves for each treatment arm for a visual description of the difference among arms. The Brookmeyer-Crowley methodology will be used to construct the 95% CI for the median OS ([Brookmeyer and Crowley 1982](#)).

4.4.2 Secondary Efficacy Endpoints

4.4.2.1 Progression-Free Survival

PFS is defined as the time between the date of randomization and the date of first documented disease progression or death, whichever occurs first. Disease progression will be determined on the basis of investigator assessment using RECIST v1.1. Data for patients who are alive and have not experienced disease progression at the time of analysis will be censored at the date of last tumor assessment. Data from patients with no post-baseline tumor assessment will be censored at the randomization date plus 1 day. PFS will be analyzed using the same methods as described in Section 4.4.1.

4.4.2.2 Objective Response Rate

ORR is defined as the proportion of patients who had a confirmed objective response of CR or PR assessed by the investigator according to the RECIST v1.1. The analysis population for ORR will be all randomized patients with measurable disease at baseline (i.e., patients with at least one measurable lesion according to RECIST v1.1 based on investigator assessment). An estimate of ORR and its 95% CI will be calculated using the Clopper-Pearson method for each treatment arm.

Treatment difference in ORR will be tested using the stratified Cochrane-Mantel-Haenszel test, stratified by the same factors used in the OS analysis, and a 95% Hauck-Anderson CI will be calculated for the difference in ORR between treatment arms.

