Because of the high unmet medical need in heavily pretreated advanced mCRC, where OS is only 6 months, several clinical studies have tested checkpoint inhibitors in this

setting with disappointing results ([Brahmer et al. 2012](#); [Topalian et al. 2012](#); [Poulin-Costello et al. 2013](#)).

Recently, immune checkpoint inhibitors have been shown to have clinical benefit in microsatellite (MSI) unstable mCRC but not in MSI stable cohorts ([Le et al. 2015](#)). This preferential effect of checkpoint inhibitors on MSI-high CRCs has been postulated to be due to an increase in neo-antigens from a greater somatic mutation load. This increase in somatic mutations amplifies upstream pathways required for an immune response, such as recruitment of immune effector or antigen presenting cells ([Llosa et al. 2015](#); [Zhang et al. 2015](#)). Furthermore, the mismatch repair-deficient cancers have increased CD8-positive T cells and PD-L1 expression in the tumor, which may explain why they are responsive to checkpoint inhibitors ([Li et al. 2015](#); [Smedt et al. 2015](#)).

One potential mechanism to convert otherwise resistant cancers is to recruit immune cells to the tumor sites so that the anti-PD L1 can be effective in activating the local immune system against the cancer cells. Nonclinical models suggest that MEK inhibition may have pleiotropic effects that could impact the tumor immune microenvironment, as the MAPK pathway has been implicated in the immune resistance of tumors and inhibition of this pathway can lead to increase CD8-positive T-cell infiltration ([Kakavand et al. 2015](#); [Liu et al. 2015](#)).

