6. STATISTICAL CONSIDERATIONS AND ANALYSIS PLAN

This is a randomized, Phase III, global, multicenter, open-label study designed to evaluate the safety and efficacy of cobimetinib plus atezolizumab and atezolizumab monotherapy as compared to treatment with regorafenib in approximately 360 patients with unresectable locally advanced or metastatic colorectal adenocarcinoma.

The efficacy analyses of OS, PFS, and ORR will be performed on all randomized patients (i.e., intent to treat [ITT]) irrespective of whether the assigned treatment was actually received. DOR will be assessed in patients who have an objective response. For all efficacy analyses, patients will be grouped according to the treatment assigned at randomization.

The safety population will include all randomized patients who received any amount of study drug. Patients who are randomized into the study but do not receive any amount of study drug will not be included in the safety population. For safety analyses, patients will be grouped according to whether any amount of cobimetinib and/or atezolizumab was received, including the case when study drug (cobimetinib and/or atezolizumab) was received in error.

Statistical details for all the analyses will be documented in the Statistical Analysis Plan.

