6.4.2 Secondary Efficacy Endpoints

The secondary endpoints include investigator-assessed PFS, ORR, and DOR per RECIST v1.1. The analyses of PFS, ORR, and DOR will take place at the time of the OS analysis.

PFS is defined as the time between date of randomization and the date of first documented disease progression or death, whichever occurs first. Disease progression will be determined based on investigator assessment using RECIST v1.1. Data from patients who have not experienced disease progression or death will be censored at the last tumor assessment date and known to be free of disease progression. Data from patients with no post-baseline tumor assessment will be censored at the randomization date plus 1 day. Comparisons with respect to PFS between the two treatment arms will be tested based on a 2-sided stratified log-rank test. The HR for PFS will be estimated using a stratified Cox model. Two-sided 95% CIs for the HR will be provided. Stratified analyses will incorporate the same stratification factors as for the analysis of OS.

Results from an unstratified log-rank test and the unstratified HR will also be presented. Kaplan-Meier methodology will be used to estimate median PFS for each treatment arm, and the Kaplan-Meier curves will be provided.

ORR is defined as the proportion of patients who had a confirmed objective response of CR or PR assessed by the investigator according to the RECIST v1.1. An estimate of ORR and its 95% CI will be calculated using the Clopper-Pearson method for each treatment arm.

Treatment difference in ORR will be tested using the stratified Cochrane-Mantel-Haenszel test, stratified by the same factors used in the OS analysis, and a 95% Hauck-Anderson CI will be calculated for the difference in ORR between treatment arms.

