Table 2	Operating Characteristics for the Comparison of Arm A versus Arm B with Approximately 165 Overall Survival Events	12

LIST OF FIGURES

Figure 1	Study Schema.....	7
Figure 2	Overview of Hierarchical Testing Sequence for Type 1 Error a Control (2-Sided).....	10

LIST OF APPENDICES

Appendix 1	Protocol Synopsis	22
Appendix 2	Schedule of Assessments.....	33
Appendix 3	Schedule of Pharmacokinetic and Immunogenicity Samples.....	44
Appendix 4	Internal Monitoring Committee Charter	45

1. **BACKGROUND**

This Statistical Analysis Plan (SAP) provides details of the planned analyses and statistical methods for Study GO30182 (IMblaze370): A Phase III, open-label, multicenter, three-arm, randomized study to investigate the efficacy and safety of cobimetinib plus atezolizumab and atezolizumab monotherapy versus regorafenib in patients with previously treated unresectable locally advanced or metastatic colorectal adenocarcinoma. The background for the study can be found in the study protocol.

It is anticipated that positive results from Study GO30182 will support the submission of filing applications globally for the use of cobimetinib plus atezolizumab for the treatment of patients with chemotherapy-refractory, unresectable, locally advanced or metastatic colorectal cancer. For purposes of registration, the analyses outlined in this SAP will supersede those specified in the protocol.

2. **STUDY DESIGN**

This is a Phase III, multicenter, open-label, three-arm, randomized study in patients with unresectable locally advanced or metastatic colorectal cancer (mCRC) who have received at least two prior regimens of cytotoxic chemotherapy for metastatic disease. The study compares regorafenib, a standard-of-care therapy in this setting, with cobimetinib plus atezolizumab and atezolizumab monotherapy.

[figure not shown]
This study will be conducted globally, and approximately 360 patients will be randomized in a 2:1:1 ratio to one of the following treatments:

- Arm A: cobimetinib 60 mg orally on Days 1–21 plus atezolizumab 840 mg intravenous (IV) on Day 1 and Day 15 in a 28-day cycle (n=approximately 180), or
- Arm B: atezolizumab monotherapy 1200 mg IV on Day 1 in a 21-day cycle (n=approximately 90), or
- Arm C: regorafenib 160 mg orally on Days 1–21 in a 28-day cycle (n=approximately 90).

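### The Hauck-Anderson interval for the ORR difference collapses when an arm has zero or near-zero responders, and the plan names no alternative for that case

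*SAP*

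**What the plan says.** For ORR, SAP Section 4.4.2.2 specifies three things: a Clopper-Pearson 95% interval in each arm, a CMH test stratified by the factors used for OS, "and a 95% Hauck-Anderson CI will be calculated for the difference in ORR between treatment arms". Protocol Section 6.4.2 has the same set and also states that "a 95% Hauck-Anderson CI will be calculated for the difference in ORR between treatment arms". Neither text says what happens when an arm has no responders or only one or two.

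The denominators differ. In the SAP, "The analysis population for ORR will be all randomized patients with measurable disease at baseline". In Protocol Section 6, "The efficacy analyses of OS, PFS, and ORR will be performed on all randomized patients". Arms B and C are planned at about 90 patients each (SAP Section 2), so the denominator is at most about 90 per arm under either rule.

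ORR is a secondary endpoint. The SAP's amendment rationale keeps only the two OS comparisons in the testing hierarchy, and states that the secondary analyses will still be submitted to health authorities.

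**The concern.** Hauck-Anderson is a Wald-type interval: it estimates each arm's variance from the observed proportion and adds a small continuity term. When an arm has no responders its estimated variance is zero, although the uncertainty about its true rate is not. The reported interval can then claim much more precision than the data hold.

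The protocol's background makes this worth planning for. Section 1.6 reports that checkpoint inhibitors showed "clinical benefit in microsatellite (MSI) unstable mCRC but not in MSI stable cohorts", and Section 3.1 limits MSI-high enrollment to about 5%, which is 4 or 5 patients in an arm of 90. Few responders in Arm B is therefore a realistic possibility.

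At stake is the stated precision of a secondary endpoint. This has some weight because of SAP Section 4.4.4: if Arm A v Arm C is significant for OS and Arm B v Arm C is not, atezolizumab's contribution is judged on all endpoints from estimates and confidence intervals, with no hypothesis test. In that situation intervals are the evidence.

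**Working it through.** The documents state no expected ORR, ORR power or interval width for this comparison, so there is no plan figure to reproduce. The inputs from the documents are n = 90 per arm and a two-sided 95% level (z = 1.96). All true response rates below are assumptions.

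**Formula.** With observed proportions p1 and p2 and q = 1 − p, Hauck-Anderson is (p1 − p2) ± {1/(2·min n) + 1.96·√[p1q1/(n1 − 1) + p2q2/(n2 − 1)]}.

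**No responders in either arm, 0/90 v 0/90.**
- Hauck-Anderson: the root is 0, leaving 1/180 = 0.0056, or ±0.56 points.
- Miettinen-Nurminen: at a difference d the constrained estimates are d and 0. The limit solves d² = 3.84·[d(1 − d)/90]·(180/179). With k = 3.84 × 180/(90 × 179) = 0.0429, d = k/(1 + k) = 0.0412, or ±4.1 points.
- The SAP's own Clopper-Pearson upper limit for 0/90: 1 − 0.025^(1/90) = 0.040, or 4.0% in each arm.

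If only 80 patients per arm had measurable disease (an assumed figure), these become ±0.62 points, ±4.6 points and 4.5%.

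**One responder, 1/90 v 0/90.** The difference is 1.11 points. The half-width is 0.0056 + 1.96·√(0.01099/89) = 0.0056 + 0.0218 = 0.0273. Hauck-Anderson gives −1.6 to 3.8 points; Miettinen-Nurminen gives −3.0 to 6.1.

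**Exact coverage.** Width alone does not show that an interval is wrong, so coverage was found by summing the two binomial distributions over all outcomes, 90 v 90.

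| Assumed true ORRs | Hauck-Anderson | Miettinen-Nurminen |
|---|---|---|
| 2% v 0.5% | 88.3% | 99.2% |
| 2% v 1% | 92.3% | 97.6% |
| 3% v 1% | 93.3% | 96.3% |

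For rates where Hauck-Anderson does well: 1% v 1% gives 99.8%, 2% v 2% gives 98.7%, 3% v 2% gives 96.7%, 4% v 1% gives 96.4% and 5% v 2% gives 96.6%.

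**Where the misses come from.** At 2% v 0.5% the true difference is 1.5 points. The 0 v 0 outcome has an upper limit of 0.56 and so misses it. Its probability is 0.98^90 × 0.995^90 = 0.162 × 0.637 = 0.103, which is most of the 11.7% total miss. Nearly all of that total (11.6%) lies on one side, where 2.5% is nominal. At 1% v 0.5% the true difference of 0.5 points lies inside ±0.56, and coverage is 99.9%.

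**Over a grid of rates, 90 v 90.** With both true rates between 0.1% and 2%, mean coverage is 91.1% and half the points fall below 95%. With both between 2% and 5%, the mean is 97.1% and the minimum 95.1% (94.5% with 80 per arm).

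**Arm A v Arm C, 180 v 90.** With Arm A at 13%, the partial response rate that Protocol Section 1.8 gives for the combination in KRAS-mutated disease, and Arm C at 0.5% to 2%, coverage is 96.2% to 96.8%. With Arm A at 8%, 5% or 3% and Arm C at 1%, it is 97.4% to 98.5%.

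**The case against.** The strongest reply is that the sparse case is not shown to be the expected one. The documents give no ORR for regorafenib, and none for atezolizumab monotherapy in colorectal cancer. Protocol Section 1.4.3 reports 18% pooled over tumor types and lists colorectal cancer among those with responses. Section 3.3.5 suggests that activity may extend beyond MSI-high tumors. The design itself assumes an OS hazard ratio of 0.61 for Arm B. This stands: few responders is plausible, not likely on the documents.

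A second reply is that the shortfall needs particular conditions and is modest in two of the three cases tabulated. This also stands. Part of the gap in width reflects the conservatism of the score interval, which covers 99.2% in the first case.

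A third reply is that little depends on this interval. ORR is outside the alpha hierarchy, no decision rule uses the interval, and the per-arm Clopper-Pearson intervals would show a reader the real uncertainty. That limits the consequence. It does not explain why the plan should report a difference known to ±0.6 points beside two rates each known only to within 4.0%.

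A reader might infer three stronger things that the material does not support:
- That Hauck-Anderson is too narrow whenever responses are few. It covers 99.8% at 1% v 1% and 96.4% at 4% v 1%.
- That a ±0.6 interval at 0 v 0 is itself a coverage failure. If the true rates are equal, that interval contains the true difference.
- That Arm A v Arm C is compromised. In the cases worked with Arm A responding more often, it is not.

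**Conclusion.** The point holds in a limited form. At zero or near-zero responders the specified interval shrinks toward ±1/(2n), and the plan has no provision for this. The 0/90 v 0/90 result, ±0.6 against ±4.1 points, is plain arithmetic and rests only on the planned arm size. The loss of coverage rests on assumed unequal true rates with one arm below about 2%, and even there it is not universal. Where it occurs, tabulated coverage is 88.3% to 93.3% instead of 95%. The comparison exposed is Arm B v Arm C, and only if responses there prove that rare. The effect is confined to the reported precision of a secondary endpoint. The OS tests and overall type I error are untouched. It merits a change because the change is very cheap, not because a trial conclusion depends on it.

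**What to change.** In SAP Section 4.4.2.2, and to match in Protocol Section 6.4.2, replace the Hauck-Anderson interval with a 95% Miettinen-Nurminen score interval for the difference in ORR. A version stratified by the two CMH factors would align the interval with the test, but it is optional: the figures above are for the unstratified interval, and the stratified one was not evaluated at these sparse counts.

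The cost is one line of text in each document. The downside is a visibly wider interval when responders are few, for example ±4.1 in place of ±0.6 points at 0/90 v 0/90. At about 13% v 1% the two methods agree, so little is lost where responses are common.
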